### 3. OBJECTIVE(S) AND ENDPOINT(S)

Objectives	Endpoints
Primary	

 
To investigate the safety and tolerability of 60 mg three times daily doses of GSK2982772 in subjects with moderate to severe Rheumatoid Arthritis.
 
	
 
Adverse events.
 
Clinical laboratory values (clinical chemistry, haematology and urinalysis).
 
Vital sign measurements (blood pressure, heart rate, respiratory rate, and body temperature).
 
12-Lead ECG monitoring.
 

Secondary	

 
To investigate the plasma concentrations of GSK2982772 following 60 mg three times daily doses of GSK2982772 in subjects with moderate to severe Rheumatoid Arthritis.
 
	
 
Pre-dose concentrations of GSK2982772 on Days 8, and 43 (Week 6).
 
Post-dose concentrations of GSK2982772 on Days 1, 8, and 43 (Week 6) at 1, 2, 4 and 6 hours.
 
Trough concentrations on Day 85 (Week 12).
 

 
To investigate the effect of 60 mg three times daily doses of GSK2982772 on inflammatory biomarkers in blood subjects with moderate to severe Rheumatoid Arthritis.
 
	
 
Change from baseline in blood inflammatory markers (e.g., may include but not limited to CRP, IL6, MMP-1, MMP-3, MMP-13, TIMP-1, MCP-1, MIF, MRP8/14 and other markers encompassed by Vectra DA).
 

 
To investigate the effect of 60 mg three times daily doses of GSK2982772 on bone and synovial parameters as measured by MRI and DCE-MRI in subjects with moderate to severe Rheumatoid Arthritis.
 
	
 
Change from baseline in MRI parameters in the most affected hand/wrist. MRI parameters may include assessment of bone erosions, synovitis, bone oedema and joint space narrowing as assessed in the OMERACT-RAMRIS (Outcome Measures in Rheumatology, Rheumatoid Arthritis Magnetic Resonance Image Scoring System) scoring system, the RAMRIQ (rheumatoid arthritis MRI quantitative) scoring system, the modified CARLOS (Cartilage Loss Scoring System) and additional exploratory endpoints as data permit.
 
Change from baseline in synovial inflammation as measured by dynamic contrast enhanced (DCE)-MRI in the most affected hand/wrist:
 

Objectives	Endpoints

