#### 4.5. Dose Justification

The initial selection of the 60 mg BID dose being tested in this study is based on the safety, PK, and PD data from the First Time in Human (FTiH) study, 200975. GSK2982772 administered at 60 mg BID for 14 days was well tolerated and no safety concerns were identified. A BID dosing regimen was initially selected over a QD dosing regimen due to the short half-life of GSK2982772 in humans (~2h). Based on preliminary PK/PD modelling of ex-vivo RIP1 target engagement and GSK2982772 concentrations from the multiple dose ascending part of Study 200975, a 60 mg BID dose was predicted to have on average 95% RIP1 target engagement in blood and approximately 90% of subjects will have >90% target engagement in blood at  $C_{min}$  using a novel in-house ex-vivo PD/target engagement assay based solely on the TNF pathway which is believed to be a key component of the RIP1 pathway.

However, based on final PK/PD modelling from the full repeat dose part of the Study 200975 (up to 120 mg BID), a 60 mg BID dose is now predicted to have on average 99% RIP1 target engagement in blood and approximately 90% of subjects will have >85% target engagement at  $C_{min}$ . This is lower than our target of achieving >90% target engagement in at least 90% of subjects at  $C_{min}$ . Therefore, a 60 mg TID cohort is now being proposed.

The  $C_{min}$  values at 60 mg TID are predicted to be approximately 3.5 fold higher than for 60 mg BID. Using the final PK/PD, a 60 mg TID dose is predicted to have on average 99% RIP1 target engagement in blood and approximately 90% of subjects will have >96% target engagement at  $C_{min}$ . No data are currently available about the distribution of GSK2892772 into the synovium. Based on data in non-steroidal anti-inflammatory drugs (NSAIDs), the synovial fluid concentrations fluctuate to a much lesser extent than those in plasma [Netter, 1989]. Peak drug concentrations are generally lower in synovial fluid but are similar to plasma at later time points. Assuming the same is true for GSK2982772, a 60 mg TID dose should provide similar RIP1 target engagement at the site of action as predicted in blood.

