	
Clinical data: In the FTiH study, no SAEs were reported. One subject experienced an Adverse Effect (AE) herpes zoster approximately 27 days after receiving his last dose with GSK2982772 or placebo. The blinded Investigator determined this to be potentially drug-related.
	
C, and excluded from the study if positive.
 
Subject Monitoring:
 
 
Subjects will be monitored for signs of infection.
 
See Individual Stopping Criteria for atypical or opportunistic infections (Section 5.4.1).
 

Vaccinations	
There is a theoretical risk that GSK2982772 could decrease an individual's immune response to vaccines or allow symptoms to develop following vaccination with a live vaccine when administered while on therapy.
	
Subject Selection:
 
 
Attenuated or live vaccines should not be administered to subjects from 30 days prior to the first dose of GSK2982772, during the study and for 5 half-lives plus 30 days (total 32 days) after GSK2982772 is discontinued.
 
If indicated, non-live vaccines (e.g. inactivated influenza vaccines) may be administered while receiving GSK2982772 based on a treating physician assessment of the benefit:risk (e.g., risk of theoretical decreased responsiveness).
 
Investigators will be expected to have followed local and/or national guidelines with respect to vaccinations, including against influenza and pneumococcus, in subjects with RA.
 

Respiratory	
Non-clinical data: In the single dose Safety Cardiovascular (CV) and Respiratory Study in monkeys, a decrease in minute volume (MV) and respiratory rate was observed at all doses (10, 100, and 300 mg/kg). These findings were noted to be reversible and mild in severity In a 14-day repeat dose Safety Respiratory Study in monkeys, no respiratory effects on total pulmonary ventilation (minute volume) or respiratory rate were observed at doses of 1 or 10 mg/kg/day. See IB for GSK2982772 [GlaxoSmithKline Document Number 2014N204126_02].
	
Subject Monitoring:
 
 
Subjects should be monitored for standard respiratory-related adverse events.
 
Vital signs will be monitored during study visits.
 

Potential Risk of Clinical Significance	Summary of Data/Rationale for Risk	Mitigation Strategy

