## 7. STUDY ASSESSMENTS AND PROCEDURES

Protocol waivers or exemptions are not allowed with the exception of immediate safety concerns. Therefore, adherence to the study design requirements, including those specified in the Time and Events Table (Section 7.1), are essential and required for study conduct.

Supplementary study conduct information not mandated to be present in this protocol is provided in the SRM and laboratory manual. The SRM will provide the site personnel with administrative and detailed technical information that does not impact subject safety.

This section lists the procedures and parameters of each planned study assessment. The timing of each assessment is listed in the Time and Events Table Section 7.1

- At study visits, the Patient Reported Outcomes (PROs) should be completed prior to any other study assessments.
- The timing and number of planned study assessments, including safety, pharmacokinetic, pharmacodynamic/biomarker or others assessments may be altered during the course of the study based on newly available data (e.g., to obtain data closer to the time of peak concentrations) to ensure appropriate monitoring.
- The change in timing or addition of time points for any planned study assessments must be documented in a Note to File which is approved by the relevant GSK study team member and then archived in the study sponsor and site study files, but this will not constitute a protocol amendment.
- No more than 500 mL of blood will be collected over the duration of the study, including any extra assessments that may be required.
- The Institutional Review Board/Independent Ethics Committee (IRB/IEC) will be informed of any safety issues that require alteration of the safety monitoring scheme or amendment of the Informed Consent Form.

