## 7.1. Time and Events Table

Procedures	Screening (-30)	Treatment Period 													Early Withdrawal 	Follow Up (±3) 
		Day 1	Day 8 (±3)	Day 15 (±3)	Day 22 (±3)	Day 29 (±3)	Day 36 (±3)	Day 43 (±3) (week 6)	Day 50 (±3)	Day 57 (±3)	Day 64 (±3)	Day 71 (±3)	Day 78 (±3)	Day 85 (+2) (week 12)		
Site Visit	X	X	X	X		X		X		X		X		X	X	X
Phone call					X		X		X		X		X			
General/Safety Assessments and Procedures																
Informed Consent	X															
Subject Demography	X															
Full medical history 	X															
Inclusion/Exclusion Criteria	X															
Full physical exam 	X													X	X	X
Brief physical exam		X 		X		X		X 		X		X				
Vital signs (BP, HR, RR, temperature)	X	X 	X	X		X		X 		X		X		X	X	X
12-lead ECG	X 	X 	X	X		X		X 		X		X		X	X	X
Concomitant medication review & AE reporting/SAEs 	X-----X															
PROs/Questionnaires/Diaries/Disease Assessments and Procedures																
Columbia Suicide Severity Rating Scale (C-SSRS)	X	X 						X 						X	X	
FACIT-fatigue; RA Symptom and Impact Diary 		X 						X 						X	X	
HAQ-DI; Patient Assessment of joint pain 		X 		X		X		X 		X		X		X	X	
Patient Global Assessment (PtGA) 	X	X 		X		X		X 		X		X		X	X	
Tender (28) & Swollen (28) joint count	X	X 		X		X		X 		X		X		X	X	
Physician Global Assessment (PGA)		X 		X		X		X 		X		X		X	X	
MRI/DCE-MRI 		X 						X 						X 	X 	

Procedures	Screening (-30)	Treatment Period 												Early Withdrawal 	Follow Up (±3) 	
		Day 1	Day 8 (±3)	Day 15 (±3)	Day 22 (±3)	Day 29 (±3)	Day 36 (±3)	Day 43 (±3) (week 6)	Day 50 (±3)	Day 57 (±3)	Day 64 (±3)	Day 71 (±3)	Day 78 (±3)			Day 85 (+2) (week 12)
Study Treatment																
Randomisation		X														
Study medication (three times daily) 		X	-----X													
Dispensing of study medication		X			X				X							
Dispensing of diary cards		X	X	X		X		X		X		X				
Collection and review of diary cards			X	X		X		X		X		X		X	X	
Laboratory (Safety) Assessments and Procedures																

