**Footnotes:**

1. Full medical history (includes past and current conditions, medication history, substance usage, and family history of premature CV disease).
2. Full physical exam (includes height/weight at screening, height not measured at later time points).
3. Triplicate ECG to be performed at screening only.
4. Pre-dose.
5. Any SAEs assessed as related to study participation (e.g., protocol-mandated procedures, invasive tests, or change in existing therapy) or related to a GSK product will be recorded from the time a subject consents to participate in the study up to and including any follow-up. AEs will be collected from the start of Study Treatment until the follow-up contact. On Days 22, 36, 50, 64, and 78, subjects will be questioned about their general health status via phone call.
6. All PRO assessments should be conducted on site before any tests, procedures, or assessments, to avoid influencing the subjects' perception.
7. DCE-MRI will be performed on all subjects, provided that sites have DCE-MRI capability and experience (e.g., hardware and software requirements). If sites do not have DCE-MRI capability or experience, a regular MRI will be performed of the affected hand/wrist. If the same joint is used for MRI and synovial biopsy, MRI should be performed before biopsy (if applicable).
8. Subjects must take study medication three times a day approximately 8 hours apart. Exact time of dosing to be recorded in diary cards. On Day 1, the first study dose will be administered at the site. On Days 8, 43 and 85 only, subjects must not take their medication at home in the morning. Subjects will complete pre-dose assessments and then will be administered their morning dose of medication at site on Days 8 and 43. On Day 85, subjects are no longer receiving study medication.
9. If urine pregnancy test is positive, a confirmatory serum pregnancy test must be performed.
10. Haematology and chemistry only. No urinalysis required on Days 29, 57 and 71. When clinical laboratory samples are taken on the same day as the MRI, the samples should be taken first prior to the administration of the contrast fluid with MRI. If this is not feasible (i.e. MRI is performed first), it is recommended that a separate IV catheter or straight venipuncture be performed in the *opposite* arm to where the MRI contrast fluid was administered.

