11. Blood samples for inflammatory biomarkers, mRNA and target engagement. See laboratory manual for full details on sample collection, handling and shipment.
12. PK blood samples for GSK2982772 will be taken pre-dose on Days 8 and 43. Post-dose serial PK samples will be taken on Days 1, 8 and Day 43 at the following time points: 1, 2, 4, and 6 hours. A trough PK sample will be taken on Day 85 or at Early Withdrawal.
13. Only applicable if subjects are on MTX: PK blood samples for MTX will be taken pre-dose GSK2982772 on Day 1 (MTX alone), on Days 8 and 43 (MTX + GSK2982772). Subjects who are on MTX should ideally take their MTX dose on the same day of the week at approximately the same time of the day throughout the study. In addition, the Day 1, 8 and 43 visits should ideally be on the same day of the week.
14. A PGx blood sample is collected at the baseline visit, after the subject has been randomised and provided informed consent for genetic research. If the sample is not collected at the baseline visit, it can be collected at any time during the study after randomisation.
15. Synovial biopsies are optional.
16. Biopsy (if applicable) and MRI only are required at Early Withdrawal visit if subject withdraws after at least 14 days of treatment and prior to Day 43. If a subject withdraws between Days 43 and 57, an MRI is not required at the Early Withdrawal visit. If a subject withdraws on Day 57 or after, an MRI should be performed at the Early Withdrawal visit. A window allowance of  $\pm 3$  days of Early Withdrawal visit is allowed to perform the MRI.
17. Visit windows during the treatment period are relative to Day 1.
18. If a subject withdraws from the study, every effort will be made for the subject to complete an Early Withdrawal visit prior to the Follow Up visit.
19. Follow-up visit should be completed 28 days ( $\pm 3$  days) after the last dose of study medication.
20. MRI (and if applicable; a biopsy) may be performed during the screening window as an additional visit (if required) up to 7 days before Day 1 to allow sites flexibility in scheduling. The MRI must be completed prior to synovial biopsy (if performed on the same joint). The site should be reasonably confident that the subject has fully qualified for the study (e.g., screening clinical labs, vital signs, physical examination, etc.) before the MRI (and if applicable: a biopsy) is/are performed.

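### No ECG or vital-sign reading in the treatment period is set at a fixed time after a dose, although both are primary safety endpoints of a drug with a half-life of about 2 hours

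*Protocol*

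**What the plan says.** Section 3 lists "12-Lead ECG monitoring" and "Vital sign measurements (blood pressure, heart rate, respiratory rate, and body temperature" among the primary safety endpoints.

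In the Time and Events Table (Section 7.1), the ECG and vital-sign rows have the same pattern over the treatment period. Day 1 and Day 43 carry footnote 4, meaning pre-dose. Days 8, 15, 29, 57, 71 and 85 carry no timing mark.

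Footnote 8 withholds the morning home dose on Days 8, 43 and 85 only. It then says: "Subjects will complete pre-dose assessments and then will be administered their morning dose of medication at site on Days 8 and 43". It adds that subjects are off study medication by Day 85, and footnote 12 describes that day's PK sample as a trough. Footnote 12 also states: "Post-dose serial PK samples will be taken on Days 1, 8 and Day 43", at 1, 2, 4 and 6 hours.

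Sections 7.3.4 and 7.3.5 specify position, rest and number of recordings, but no time relative to dose. Section 4.5 explains that BID was first chosen over once-daily dosing "due to the short half-life of GSK2982772 in humans (~2h").

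Section 7 permits the timing of assessments to be altered, for example to be nearer to peak concentration, through a Note to File. Section 7.3 permits extra safety time points. Neither schedules one.

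**The concern.** If a drug effect on QTc, heart rate, blood pressure or respiratory rate follows plasma concentration, it is easiest to see near peak and hardest to see at the end of a dosing interval. The plan fixes the dose state of only two readings after Day 1, and both are at the low end.

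At the visits with a witnessed dose and measured post-dose concentrations, no ECG or vital-sign reading is assigned to follow the dose. The study could therefore end without one reading of either endpoint that is known by design to sit beside a measured near-peak concentration. A clean Day 43 or Day 85 result would say little about effects at peak.

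The point has some specific relevance. Section 4.6.1 reports that in a single-dose monkey study "a decrease in minute volume (MV) and respiratory rate was observed at all doses (10, 100, and 300 mg/kg"), and it relies partly on vital signs at visits to monitor for respiratory effects.

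**Working it through.** **Inputs.** Half-life about 2 h, and a Cmin at 60 mg TID about 3.5 times that at 60 mg BID (Section 4.5). Dosing interval about 8 h for TID and about 12 h for BID (Section 4.2.2). PK samples at 1, 2, 4 and 6 h (Section 7.1, footnote 12). The documents give no time of peak (tmax), so I assume 1 to 4 h, which lies within the PK sampling times.

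**Step 1: is the stated half-life consistent with the stated trough ratio?** For a one-compartment bolus model at steady state, the TID:BID trough ratio is (2^(12/h) − 1) / (2^(8/h) − 1), with h the half-life in hours.
- h = 2: (64 − 1)/(16 − 1) = 63/15 = 4.2.
- h = 2.34: 3.5, the protocol's figure.

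A half-life of about 2 h and a ratio of about 3.5 therefore agree after rounding. Both values of h are carried forward.

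**Step 2: what does the table fix?** Treatment-period ECG and vital-sign readings after Day 1:

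| Day | Dose state set by the protocol |
|---|---|
| 8 | Home dose withheld, site dose witnessed; reading time not set |
| 15, 29, 57, 71 | Home dose possible; reading time not set |
| 43 | Pre-dose |
| 85 | After the last dose, trough |

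Of seven readings, one is fixed pre-dose, one follows the last dose, and five have no set time. None has a set post-dose time. Day 1 is pre-dose, as a baseline should be. The early-withdrawal and follow-up readings are outside this count.

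**Step 3: how low is a pre-dose concentration?** Concentration as a share of peak = 2^(−(t − tmax)/h), with t the hours since the last dose.

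| h | tmax | t = 8 h | t = 12 h |
|---|---|---|---|
| 2 | 1 | 2^−3.5 = 8.8% | 2^−5.5 = 2.2% |
| 2 | 2 | 2^−3 = 12.5% | 2^−5 = 3.1% |
| 2 | 4 | 2^−2 = 25% | 2^−4 = 6.2% |
| 2.34 | 1 | 12.6% | 3.9% |
| 2.34 | 2 | 16.9% | 5.2% |
| 2.34 | 4 | 30.6% | 9.4% |

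At the stated half-life, a pre-dose reading is at about 9–25% of peak after 8 h, and about 2–6% after 12 h. The 12 h column applies to BID subjects, and to a TID subject whose withheld morning dose stretches the gap that far. The longer half-life raises the 8 h range to about 13–31%, which does not change the conclusion.

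**Scope.** The table read here is that of Amendment 3. The text shown for Amendment 4 (Germany) stops before its own table, and its stated changes concern haematology criteria only.

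**The case against.** The strongest case on the other side has five parts.

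- **Readings near peak are possible.** The home dose is withheld only on Days 8, 43 and 85, so the Day 15, 29, 57 and 71 readings can follow a normal morning dose. Diary cards record dose times, so time since dose may be recoverable. Day 8 ECG and vital signs are not marked pre-dose, whereas the Day 8 PK entries are, so a post-dose Day 8 reading already complies. All of this stands. A reader might infer that every reading is at trough, or that none can be near peak; the table does not support that. What remains is that nothing requires a reading at a known post-dose time, and the four home-dose visits have no PK sample.
- **Trough is not pharmacologically quiet.** Section 4.5 predicts average RIP1 engagement of 99% on TID, with about 90% of subjects above 96% at Cmin. An effect mediated by the target should therefore be visible pre-dose. This stands and limits the point to effects driven by plasma concentration.
- **The respiratory evidence is largely reassuring.** Section 4.6.1 reports no respiratory effect in a 14-day monkey study at 1 or 10 mg/kg/day. It also reports none attributed to drug in 36 healthy men dosed for 14 days under intensive respiratory monitoring. A reader might infer from the single-dose monkey finding alone that a known hazard goes unmonitored; the full entry does not support that.
- **The plan has a way to adapt.** Section 7 foresees moving assessments ("e.g., to obtain data closer to the time of peak concentrations) to ensure appropriate monitoring"), and Section 7.3 allows added time points. Both are discretionary. They show that the remedy is available, not that it is scheduled.
- **A pre-dose Day 43 reading has value.** It matches the Day 1 baseline in dose state, and the QTc criteria in Section 5.4.4 include a change from baseline. This is a good reason to leave Day 43 alone.

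**Conclusion.** The point holds as a gap in assessment timing; it is neither an error nor a contradiction. None of the seven treatment-period readings of two primary safety endpoints after Day 1 has a set post-dose time. The two whose dose state is known are at the end of a dosing interval, at roughly 9–25% of peak concentration for an 8 h gap. That range rests on a half-life of 2 h, an assumed tmax of 1–4 h and single-exponential decline after the peak.

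A reader might compute 2^(−8/2) = 6% and call that the share of peak remaining. That counts decay from the moment of dosing rather than from the peak, and so overstates the case.

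Nor does the point undermine the safety assessment as a whole. Adverse events and laboratory values are untouched, and target-mediated effects should remain visible at trough. That subjects stay on site for six hours is inferred from the PK times and not stated. I rate this a cheap improvement, optional for the sponsor.

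**What to change.** In the Time and Events Table, add a footnote to the Day 8 ECG and vital-sign entries. It should say that they are taken after the witnessed site dose, next to one of the early post-dose PK samples, with actual dose and reading times recorded. The sponsor should choose the sample nearest the tmax seen in the first-in-human study. Keep Day 1 and Day 43 pre-dose. Day 43 could be moved in the same way if the sponsor accepts losing the mid-treatment reading matched in dose state to baseline.

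The cost is wording only: the number of ECGs, vital-sign sets, blood draws and visits is unchanged. Day 8 carries no patient-reported outcomes, so the rule that these come first at a visit is not disturbed. The downside is that Day 8 would no longer be available as a pre-dose reading, and its clock time would differ from that of Day 1.
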